#### 1 BACKGROUND AND RATIONALE

CA209648 is a randomized, global Phase 3 study of nivolumab plus ipilimumab or nivolumab in combination with fluorouracil plus cisplatin versus fluorouracil and cisplatin chemotherapy as first line-therapy in inoperable advanced, recurrent or metastatic esophageal squamous cell carcinoma (ESCC). This study will determine if nivolumab plus ipilimumab and nivolumab combined with fluorouracil plus cisplatin improve overall survival (OS) and/or progression free survival (PFS) over fluorouracil and cisplatin standard of care chemotherapy (further: chemotherapy) in subjects with ESCC whose tumors express PD-L1. Additional objectives include further characterization of the efficacy, adverse event profile, pharmacokinetics (PK), patient reported outcomes, and potential predictive biomarkers of nivolumab in combination with ipilimumab or nivolumab in combination with fluorouracil and cisplatin in subjects with ESCC.

#### **Research Hypothesis:**

- The administration of nivolumab plus ipilimumab will improve OS compared with fluorouracil and cisplatin combination in subjects with unresectable advanced, recurrent or metastatic ESCC with PD-L1 expression ≥ 1%.
- The administration of nivolumab combined with fluorouracil plus cisplatin will improve OS compared with fluorouracil and cisplatin combination alone in subjects with unresectable advanced, recurrent or metastatic ESCC with PD-L1 expression ≥ 1%.
- The administration of nivolumab plus ipilimumab will improve PFS as assessed by a blinded independent central review committee (BICR) compared with fluorouracil and cisplatin combination in subjects with unresectable advanced, recurrent or metastatic ESCC with PD-L1 expression ≥ 1%.
- The administration of nivolumab combined with fluorouracil plus cisplatin will improve PFS as assessed by a BICR compared with fluorouracil and cisplatin combination alone in subjects with unresectable advanced, recurrent or metastatic ESCC with PD-L1 expression ≥ 1%.

#### **Schedule of Analyses:**

In this study, two formal efficacy analyses are planned:

• Final PFS analysis and Interim OS analysis: For superiority of PFS in subjects who were randomized to nivolumab plus ipilimumab vs. subjects who were randomized to chemotherapy and in subjects who were randomized to nivolumab in combination with chemotherapy vs. subjects who were randomized to chemotherapy only. Analysis will be performed when 136 PFS events per BICR are observed or when a 12-month minimum follow-up (defined as the time from the date of the last patient was randomized to the clinical cutoff date) is reached if the planned number of events is unlikely to be reached among the PD-L1 expressing subjects in the chemotherapy arm. By design, 136 PFS events among the PD-L1 expressing subjects in the chemotherapy arm are expected to be reached approximately 33 months after first patient randomized. At the same time, formal interim analysis of OS will be also conducted (in case of significant results, study may be stopped). All the events observed in the locked database will be used in the final analysis of PFS, following intention-to-treat principle (Section 5).

• Final OS analysis: For superiority of OS in subjects who were randomized to nivolumab plus ipilimumab vs. subjects who were randomized to chemotherapy and in subjects who were randomized to nivolumab in combination with chemotherapy vs. subjects who were randomized to chemotherapy only. Analysis will be performed when 140 OS events are observed among the PD-L1 expressing subjects in the chemotherapy arm. This is expected to be reached approximately 49 months after first patient randomized. In the case that the observed number of OS events exceed the pre-planned number, all the events observed in the locked database will be used in the final analysis of OS, following intention-to-treat principle (Section 5).

Since each of the formal efficacy analyses will be triggered by the pre-planned number of events among the PD-L1 expressing subjects in the chemotherapy arm, the external independent statistical group supporting DMC review (Axio Research) will be utilized to conduct unblinded event tracking (the tracking plan is documented separately).

#### 2 STUDY DESCRIPTION

# 2.1 Study Design

This is a randomized Phase 3 study of nivolumab plus ipilimumab or nivolumab combined with fluorouracil plus cisplatin compared with fluorouracil and cisplatin combination in adult ( $\geq$  18 years) male and female subjects with unresectable advanced, recurrent or metastatic ESCC.

[figure not shown]
After signing the informed consent form, and upon confirmation of the subject's eligibility, subjects with unresectable advanced, recurrent or metastatic ESCC will be randomized in a 1:1:1 ratio to one of the following open-label treatments:

- Nivolumab-plus-ipilimumab (N+I) arm: Subjects will receive treatment with nivolumab 3mg/kg as a 30-minute infusion every 2 weeks and ipilimumab as a 30-minute infusion 1mg/kg every 6 weeks.
- Nivolumab-plus-chemotherapy (N+C) arm: Subjects will receive treatment with nivolumab 240mg as a 30-minute infusion on Day 1 and Day 15, fluorouracil 800mg/m²/day as an IV continuous infusion on Day 1 through Day 5 (for 5 days), and cisplatin 80mg/m² as a 30 to 120-minute infusion on Day 1 of 4-week cycle.
- Chemotherapy (CT) arm: Subjects will receive treatment with fluorouracil 800mg/m²/day as an IV continuous infusion from Day 1 through Day 5 (for 5 days), and cisplatin 80mg/m² as a 30- to 120-minute infusion on Day 1 of 4-week cycle.

Treatment with nivolumab or nivolumab with ipilimumab will be given for up to 24 months in the absence of disease progression (PD) or unacceptable toxicity. Chemotherapy will be given as per the study dosing schedule until PD or unacceptable toxicity.

Baseline and all subsequent scans will be submitted to a BICR for analysis and archiving, once the subject is randomized and throughout the study period.

Figure 2.1-1: Study Scheme

\*Treatment with nivolumab or nivolumab + ipilimumab will be limited to 2 year maximum duration

This study will consist of 3 phases: screening, treatment, and follow-up:

#### **Screening Phase**

- Begins by establishing the subject's initial eligibility and signing of the informed consent.
- Subject is enrolled using the Interactive Response Technology (IRT) system.
- Subjects must have PD-L1 IHC testing, with evaluable results, performed by the central lab during the Screening period.
- Either a formalin-fixed, paraffin-embedded (FFPE) tissue block or unstained tumor tissue sections, with an associated pathology report if available, must be submitted for biomarker evaluation prior to randomization. The tumor tissue sample may be fresh or archival if obtained within 6 months prior to randomization, and there can have been no systemic therapy (eg, adjuvant) given after the sample was obtained.
- All subjects with PD-L1 result will be randomized, but only subjects with PD-L1 expression ≥ 1% will be assessed as part of the primary objective.
- Subject is assessed for study eligibility according to the inclusion and exclusion criteria. All screening assessments and procedures must be performed within 28 days prior to randomization unless otherwise specified.

#### **Treatment Phase**

• The treatment phase begins when the treatment is assigned in the IRT. Study treatment must begin within 3 calendar days of randomization.

- Treated subjects will be evaluated for tumor assessments every 6 weeks (± 7 days) starting on Week 7 up to and including Week 48, then every 12 weeks (± 7 days) thereafter.
- Treatment with nivolumab with ipilimumab or nivolumab (Arms A and B) will be given for up to 24 months in the absence of PD or unacceptable toxicity. Chemotherapy (Arms B and C) will be given as per the study dosing schedule until PD or unacceptable toxicity. Then, the subject will enter the Follow-up Phase.

#### **Dosing in the N+I arm:**

- Nivolumab 3mg/kg will be administered IV on Day 1 and then every 2 weeks.
- Ipilimumab 1mg/kg will be administered IV on Day 1 and then every 6 weeks following the administration of nivolumab.
- When both nivolumab and ipilimumab are to be administered on the same day, nivolumab is to be administered first. The second infusion will always be ipilimumab, and will start at least 30 minutes after completion of the nivolumab infusion.
- Treatment beyond initial, investigator-assessed, RECIST 1.1-defined progression is permitted if the subject has investigator-assessed clinical benefit and is tolerating treatment.

### **Dosing in the N+C arm:**

- Nivolumab combined with fluorouracil and cisplatin will be administered IV in a 4-week cycle. Nivolumab 240mg will be administered IV every 2 weeks on Day 1 and Day 15 of each cycle. Fluorouracil 800mg/m²/day will be administered as an IV continuous infusion on Day 1 through Day 5 (for 5 days) and cisplatin 80mg/m² will be administered IV on Day 1 of 4-week cycle.
- When both nivolumab and fluorouracil and cisplatin combination are to be administered on the same day, nivolumab is to be administered first. Infusion of fluorouracil and cisplatin will start at least 30 minutes after completion of the nivolumab infusion.
- Treatment with nivolumab beyond initial, investigator-assessed, RECIST 1.1-defined PD is permitted if the subject has investigator-assessed clinical benefit and is tolerating treatment.

#### Dosing in the CT arm:

• Fluorouracil 800mg/m²/day will be administered as an IV continuous infusion on Day 1 through Day 5 (for 5 days) and cisplatin 80mg/m² will be administered IV on Day 1 of 4-week cycle.

#### Follow-up Phase

- Begins when the decision to discontinue a subject from study therapy is made (no further treatment with study therapy).
  - FU1 = 30 days from last dose ( $\pm$  7 days) or coinciding with the date of discontinuation ( $\pm$  7 days) if date of discontinuation is greater than 35 days after last dose

- FU2 = 84 days from FU1 ( $\pm$  7 days).
- Subjects who discontinue treatment for reasons other than tumor progression will continue to have tumor assessments as per the schedule for the assigned treatment arm until confirmed PD by BICR, withdrawal of consent or lost to follow-up. (For details on discontinuation of tumor assessments, see Section 2.5.)
- Subjects will be followed for all AEs until these resolve, return to baseline or are deemed irreversible. All AEs will be documented for a minimum of 100 days after the last dose of study treatment.
- After completion of the first two follow-up visits, subjects will be followed every 3 months (± 14 days) for survival via in-person visit or phone. Ad hoc survival data requests may be made during the study as well, particularly during database locks. Additional subsequent cancer therapy details such as regimen, setting of the regimen, line of therapy, start date and end date of each regimen, best response to the regimen and date of progression after second line therapy will be collected.
- The PRO questionnaires collection and biomarker sampling will continue as per time and event schedule.

# 2.2 Treatment Assignment

After the subject's initial eligibility is established and informed consent has been obtained, the subject must be enrolled into the study by entering information into the IRT system to obtain the subject number. Every subject that signs the informed consent form must be assigned a subject number in the IRT system.

Once enrolled in the IRT, subjects that have met all eligibility criteria (including the required tumor tissue received and result obtained by the central laboratory and the pathology report approved by the investigator) will be ready to be randomized through the IRT.

Subjects meeting all eligibility criteria will be randomized in a 1:1:1 ratio to either the N+I arm, or the N+C arm, or the CT arm. Randomization will be stratified by the following factors:

- 1) PD-L1 status (≥ 1% vs. < 1% [including indeterminate])\*
- 2) Region (East Asia (Japan/Korea/Taiwan [J/K/T]) vs Rest of Asia vs rest of world [RoW])
- 3) ECOG performance status (0 vs. 1).
- 4) Number of organs with metastases ( $\leq 1 \text{ vs.} \geq 2$ )

# 2.3 Blinding and Unblinding

Not applicable.

\* During enrolment, the proportion of subjects with or without PD-L1 tumor expression will be monitored, and may be re-assessed in case it does not reflect study assumptions (i.e., subjects with PD-L1 tumor expression  $\geq 1\%$  is approximately 50% of all comers).

#### 2.4 Protocol Amendments

Global amendments incorporated in the protocol with relevant changes are described in Table 2.4-1.

**Table 2.4-1:** Relevant Protocol Amendments

Amendments	Date of Issue	Summary of Major Changes	
Revised Protocol 05	29-Oct-2020	This revised protocol allows for the final PFS analysis to be triggered when 136 PFS events per BICR are observed among the PD-L1 expressing subjects in the chemotherapy arm or when at least 12 months minimum follow up is reached, if the target number of PFS events is unlikely to be reached.	
Revised Protocol 04	12-Sep-2018	This revised protocol restricts study entry to participants of previous nivolumab clinical studies where overall survival was listed as a primary or co-primary endpoint. Live /attenuated vaccines were prohibited and the inclusion criterion related to the assessment of renal function was expanded to allow the consideration of measured creatinine clearance. Cisplatin infusion times longer than 120 minutes were allowed if deemed necessary by investigator per local standard of care/local label. PFS2/TSST was added as an exploratory endpoint. The section on biomarker assessments was revised. Program updates were added and internal inconsistencies were corrected.	
Revised Protocol 03	02-Feb-2018	This revised protocol removed the procedures for the reinitiation of nivolumab $\pm$ ipilimumab treatment after disease progression for up to additional year. In addition, it added clarification to the treatment beyond progression procedures to limit treatment to a maximum duration of 24 months.	
Revised Protocol 02	25-Oct-2017	To align the protocol with the latest SmPC, simplify procedures, and provide clarifications in the protocol.	
Revised Protocol 01	21-Dec-2016	Incorporates Amendment(s) 02	
Amendment 02	21-Dec-2016	Expansion of the esophageal cohort into a 3-arm randomized Phase 3 study in first line squamous esophageal cancer. The study now includes a nivolumab plus chemotherapy arm (fluorouracil and cisplatin) and a chemotherapy alone arm in addition to the existing nivolumab and ipilimumab arm. The gastric cohort was removed.	

# 2.5 Independent Review of Progression

At the time of investigator-assessed initial radiographic progression per RECIST 1.1 in any given subject, the site must request the blinded independent central review (BICR) of progression from the third party radiology vendor.

Tumor assessments for each subject should be submitted to the radiology vendor as they are performed on an ongoing basis. The blinded, independent radiologists will review all available tumor assessments for that given subject and determine if RECIST 1.1 criteria for progression have been met. The independent assessment of whether or not the given subject met RECIST 1.1 criteria for progression will be provided to the site. Subjects whose disease progression is not confirmed

centrally will be required to continue tumor assessments (if clinically feasible) according to the protocol-specified schedule. Subsequent tumor assessments must be submitted to the third party radiology vendor for subsequent review and may be discontinued when the investigator and independent radiologists both assess the subject to have met RECIST 1.1 criteria for progression. In addition, subjects receiving treatment beyond progression must continue tumor assessments until such treatment has been discontinued.

If clinically acceptable, subsequent therapy should begin only after RECIST 1.1 progression has been assessed by BICR. For subjects who start palliative local therapy or subsequent therapy without prior assessment of RECIST 1.1 progression by central review, the Investigator must continue tumor assessments (if clinically feasible) according to the protocol-specified schedule and submit them to the third-party radiology vendor. When RECIST 1.1 progression is assessed by the investigator (whether assessed before or after the start of palliative local therapy or subsequent therapy), the BICR assessment must be requested. Tumor assessments may be discontinued when the independent radiologist assesses the subject to have met RECIST 1.1 criteria for progression.

## 2.6 Data Monitoring Committee

An independent Data Monitoring Committee (DMC) will be utilized. A DMC will be established to provide oversight of safety and efficacy considerations in CA209648. Additionally, the DMC will provide advice to the sponsor regarding actions the committee deems necessary for the continuing protection of subjects enrolled in the study. The DMC will be charged with assessing such actions in light of an acceptable benefit/risk profile for nivolumab plus ipilimumab and nivolumab plus fluorouracil and cisplatin. The DMC will act in an advisory capacity to BMS and will monitor subject safety and evaluate the available efficacy data for the study. The oncology therapeutic area of BMS has primary responsibility for design and conduct of the study.

DMC will review the safety data from the study when approximately (dependent on the accrual speed) 45 subjects (about 5% of subjects) have been treated and followed for at least 4 weeks.

The DMC will be reviewing safety data every approximately six months and will be also responsible for reviewing and making recommendations at Final PFS analysis and Interim OS analysis. (Section 1).

#### 3 OBJECTIVES

# 3.1 Primary

- To compare the OS of nivolumab plus ipilimumab to fluorouracil and cisplatin combination in subjects with PD-L1 expression ≥ 1%.
- To compare the OS of nivolumab combined with fluorouracil plus cisplatin to fluorouracil and cisplatin combination in subjects with PD-L1 expression ≥ 1%.
- To compare the PFS of nivolumab plus ipilimumab to fluorouracil and cisplatin combination as assessed by a BICR in subjects with PD-L1 expression ≥ 1%.
- To compare the PFS of nivolumab combined with fluorouracil plus cisplatin to fluorouracil and cisplatin combination as assessed by a BICR in subjects with PD-L1 expression ≥ 1%.

# 3.2 Secondary

- To compare the OS of nivolumab plus ipilimumab and nivolumab combined with fluorouracil plus cisplatin to fluorouracil and cisplatin combination in all randomized subjects.
- To compare the PFS of nivolumab plus ipilimumab and nivolumab combined with fluorouracil plus cisplatin to fluorouracil and cisplatin combination as assessed by a BICR in all randomized subjects.
- To compare the objective response rate (ORR) of nivolumab plus ipilimumab and nivolumab combined with fluorouracil plus cisplatin to fluorouracil and cisplatin combination as assessed by a BICR in subjects with PD-L1 expression ≥ 1%.
- To compare the ORR of nivolumab plus ipilimumab and nivolumab combined with fluorouracil plus cisplatin to fluorouracil and cisplatin combination as assessed by a BICR in all randomized subjects.

# 3.3 Exploratory

- To assess PFS of nivolumab plus ipilimumab and nivolumab combined with fluorouracil plus cisplatin vs fluorouracil and cisplatin combination as assessed by investigators in subjects with PD-L1 expression ≥ 1% and in all randomized subjects.
- To assess ORR of nivolumab plus ipilimumab and nivolumab combined with fluorouracil plus cisplatin vs fluorouracil and cisplatin combination as assessed by investigators in subjects with PD-L1 expression ≥ 1% and in all randomized subjects.
- To assess Duration of Response (DOR) of nivolumab plus ipilimumab or nivolumab combined with fluorouracil plus cisplatin vs fluorouracil and cisplatin combination as assessed by BICR and by investigators in subjects with PD-L1 expression ≥ 1% and in all randomized subjects.
- To assess time from randomization to the date of investigator-defined documented second objective disease progression or start of second subsequent therapy or death due to any cause, whichever comes first (PFS2/TSST) of nivolumab plus ipilimumab (Arm A) or nivolumab combined with fluorouracil plus cisplatin (Arm B) vs fluorouracil and cisplatin combination (Arm C) as assessed by investigators in subjects with PD-L1 expression ≥ 1% and in all randomized subjects.
- To assess the overall safety and tolerability of treatment with nivolumab plus ipilimumab or nivolumab combined with fluorouracil plus cisplatin vs. fluorouracil and cisplatin combination.
- To characterize the PK of nivolumab plus ipilimumab or nivolumab combined with fluorouracil plus cisplatin.
- To characterize the immunogenicity of nivolumab plus ipilimumab or nivolumab combined with fluorouracil plus cisplatin.
- To characterize immune correlates of nivolumab plus ipilimumab, nivolumab combined with fluorouracil plus cisplatin, and fluorouracil and cisplatin combination.
- To evaluate the pharmacodynamic activity of nivolumab plus ipilimumab or nivolumab combined with fluorouracil plus cisplatin in the peripheral blood.

- To explore potential biomarkers associated with clinical efficacy (OS, PFS, and ORR) and/or with incidence of adverse events of nivolumab plus ipilimumab or nivolumab combined with fluorouracil plus cisplatin by analyzing biomarker measures within the tumor microenvironment and periphery (e.g., blood, serum, plasma) in comparison to clinical outcomes.
- To assess the subject's overall health status using the EQ-5D (EQ-5D-3L) index and visual analog scale.
- To assess the subject's cancer-related quality of life using the Functional Assessment of Cancer Therapy-Esophageal (FACT-E) questionnaire and selected components, including the Esophageal Cancer Subscale (ECS) and 7-item version of the FACT-General (FACT-G7).

#### 4 ENDPOINTS

A summary of the efficacy endpoints is presented in Table 4-1.

Table 4-1: Overview of Major Efficacy Endpoints

	N+C vs CT		N+I vs CT	
	All PDL1- Expressing Subjects	All Randomized Subjects	All PDL1- Expressing Subjects	All Randomized Subjects
Primary Endpoints	OS, PFS by BICR		OS, PFS by BICR	
Secondary Endpoints	ORR by BICR	OS PFS by BICR ORR by BICR	ORR by BICR	OS PFS by BICR ORR by BICR
Exploratory Endpoints	PFS by investigator ORR by investigator DOR* PFS2/TSST by investigator	PFS by investigator ORR by investigator DOR* PFS2/TSST by investigator	PFS by investigator ORR by investigator DOR* PFS2/TSST by investigator	PFS by investigator ORR by investigator DOR* PFS2/TSST by investigator

\* By BICR and by investigator

For the definition of All PD-L1 Expressing Subjects and All Randomized Subjects, see Section 6.3.

#### 4.1 Primary Endpoints

Primary endpoints are OS and PFS in All PD-L1 expressing subjects.

# 4.1.1 Overall Survival in All PD-L1 Expressing Subjects

OS is defined as the time between the date of randomization and the date of death. For subjects without documentation of death, OS will be censored on the last date the subject was known to be alive.

[figure not shown]
# 4.1.2 Progression-Free Survival per BICR in All PD-L1 Expressing Subjects

For the purposes of the primary endpoints, PFS is as assessed by BICR in subjects with PD-L1 expressing tumors.

PFS is defined as the time from randomization to the date of the first documented PD per BICR or death due to any cause. Subjects without any baseline scan will be censored at the randomization date (regardless of death). Subjects who did not have any on-study tumor assessments and did not die (or died after initiation of the subsequent anti-cancer therapy) will be censored at the randomization date. Subjects who die without a reported prior PD per BICR (and die without start of subsequent therapy) will be considered to have progressed on the date of death. Subjects who did not have documented PD per BICR per RECIST1.1 criteria and who did not die, will be censored at the date of the last evaluable tumor assessment on or prior to initiation of the subsequent anti-cancer therapy. Subjects who started any subsequent anti-cancer therapy without a prior reported PD per BICR will be censored at the last tumor assessment on or prior to initiation of the subsequent anti-cancer therapy.

See Figure 4.1.2-1 for the graphical representation of this definition.

Figure 4.1.2-1: Graphical Representation of the Primary PFS Definition

rand = randomization, subs = subsequent therapy

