### Endpoints:

#### Primary Endpoint

Overall survival (OS) in subjects with PD-L1 expressing tumors. OS is defined as the time between the date of randomization and the date of death. For subjects without documentation of death, OS will be censored on the last date the subject was known to be alive.

Progression-free Survival (PFS) (as assessed by BICR) in subjects with PD-L1 expressing tumors. PFS is defined as the time from randomization to the date of the first documented PD per BICR or death due to any cause. Subjects who die without a reported prior PD per BICR (and die without start of subsequent therapy) will be considered to have progressed on the date of death. Subjects who did not have documented PD per BICR per RECIST1.1 criteria and who did not die, will be censored at the date of the last evaluable tumor assessment on or prior to initiation of the subsequent anti-cancer therapy. Subjects who did not have any on-study tumor assessments and did not die (or died after initiation of the subsequent anti-cancer therapy) will be censored at the randomization date. Subjects who started any subsequent anti-cancer therapy without a prior reported PD per BICR will be censored at the last tumor assessment on or prior to initiation of the subsequent anti-cancer therapy.

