## 8.3 Endpoints

### 8.3.1 Primary Endpoint

- Overall survival (OS) in subjects with PD-L1 expressing tumors. OS is defined as the time between the date of randomization and the date of death. For subjects without documentation of death, OS will be censored on the last date the subject was known to be alive.
- Progression-free Survival (PFS) (as assessed by BICR) in subjects with PD-L1 expressing tumors. PFS is defined as the time from randomization to the date of the first documented PD per BICR or death due to any cause. Subjects who die without a reported prior PD per BICR (and die without start of subsequent therapy) will be considered to have progressed on the date of death. Subjects who did not have documented PD per BICR per RECIST1.1 criteria and who did not die, will be censored at the date of the last evaluable tumor assessment on or prior to initiation of the subsequent anti-cancer therapy. Subjects who did not have any on-study tumor assessments and did not die (or died after initiation of the subsequent anti-cancer therapy) will be censored at the randomization date. Subjects who started any subsequent anti-cancer therapy without a prior reported PD per BICR will be censored at the last tumor assessment on or prior to initiation of the subsequent anti-cancer therapy.

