# 4.2.2 Progression-Free Survival per BICR in All Randomized Subjects

Progression-free survival in All Randomized subjects is defined the same way as for the primary endpoint (for subjects with PD-L1 expressing tumors).

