## 7.5.2.1 Primary Analyses

Overall survival and PFS as assessed by BICR in All PD-L1 expressing subjects will be compared between N+I vs CT and between N+C vs CT using a two-sided log rank test, stratified by the stratification factors as specified in Section 7.1.1, i.e. by

- region (J/K/T vs rest of Asia vs RoW),
- ECOG performance status (0 vs. 1),
- number of organs with metastases ( $\leq 1 \text{ vs.} \geq 2$ ).

For each comparison, the HR with its associated two-sided  $100(1-\alpha)\%$  CIs will be estimated via a stratified Cox model with treatment arm as the only covariate in the model.

Overall survival and PFS for each treatment arm will be estimated and plotted using the KM product-limit method. Median survival time along with 95% CI will be constructed based on a log-log transformed CI for the survival function.

Status of Censored Subjects

The status of subjects who are censored in the OS KM analysis will be tabulated for each randomized treatment group using following categories:

- On-study (on-treatment in follow-up);
- Off-study (lost to follow-up, withdraw consent, never treated etc.).

The status of subjects who are censored in the PFS KM analysis will be tabulated for each randomized treatment group using the following categories:

- 1) Censored on randomization date
  - a) no baseline scan
  - b) no on-study scan and no death (or death with prior subsequent therapy)
- 2) Censored on date of last tumor scan on-study
  - a) Received subsequent anti-cancer therapy
  - b) Still on treatment
  - c) In follow-up

- d) Off study
  - i) lost to follow-up
  - ii) subject withdrew consent
  - iii) other

The source of PFS event (death vs. PD) will be summarized by treatment group.

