## Sensitivity analyses for PFS to investigate alternative censoring schemes

- Analysis accounting for assessment on/after subsequent therapy: PFS will be defined similarly to the primary definition except that events (progression or death) and disease assessments that occurred on or after subsequent anti-cancer therapy will be considered (no time point truncation). This definition is considered as primary definition by EMA. The PFS accounting for subsequent therapy (primary definition, Section 4.1.2) is the primary endpoint of the study and will be the basis of the primary test to determine statistical significance.
- PFS accounting for two or more consecutively missing disease assessments prior to PFS event: This analysis will be performed only if at least 10% of PFS events have missing prior disease assessments. In case a subject has two or more consecutively missing disease assessments, the subject will be censored at the last disease assessment date prior the PFS event.
- Analysis in which progression-free subjects who are lost to follow-up for any cause will be considered as having an event at the time of the last tumor assessment date prior to loss to follow-up.

Each of the above analysis will use the same significance level as the corresponding primary analysis. Estimate of the HR, its two sided  $100(1-\alpha)\%$  CI and p-value will be presented.

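### A death in a subject with no baseline scan is a primary PFS event under the protocol but is censored at day 0 under the SAP; the effect is probably nil or very small

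*SAP*

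**What the plan says.** **Protocol.** The Synopsis and Section 8.3.1 give the same rule for death: "Subjects who die without a reported prior PD per BICR (and die without start of subsequent therapy) will be considered to have progressed", dated at the death. Section 8.3.1 censors at randomization in one situation only: "Subjects who did not have any on-study tumor assessments and did not die (or died after initiation of the subsequent anti-cancer therapy) will be" censored on that date. Neither place mentions a missing baseline scan.

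**SAP.** Section 4.1.2 repeats these rules but adds one ahead of them: "Subjects without any baseline scan will be censored at the randomization date (regardless of death". Section 4.2.2 carries the definition to the secondary endpoint: "Progression-free survival in All Randomized subjects is defined the same way as for the primary endpoint".

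Section 7.5.2.1 builds the exception into the table of censoring reasons. Category 1a reads only "no baseline scan". Category 1b reads "no on-study scan and no death (or death with prior subsequent therapy", so it has the death condition that 1a lacks.

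**The concern.** A missing baseline scan makes radiographic progression hard to judge. It does not make death hard to ascertain. The protocol counts the death as an event of a co-primary endpoint, and the SAP removes it and the subject's whole follow-up time. A program written from the SAP would give a different result from the protocol's definition for these subjects. The SAP neither states that it departs from the protocol here nor gives a reason.

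What is at stake is agreement between the two documents on a primary endpoint and, if any such deaths occur, a few events. If the mismatch is found only after unblinding, someone must choose a rule with the result in view.

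**Working it through.** **1. The same subject under each text.** Take a randomized subject with no baseline scan who dies with no earlier progression per BICR.

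| Situation at death | Protocol 8.3.1 | SAP 4.1.2 |
|---|---|---|
| No subsequent therapy started | Event on date of death | Censored at randomization |
| Subsequent therapy already started | Censored | Censored at randomization |

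Only the first row changes event status, so the contradiction is confined to deaths before any subsequent therapy.

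**2. Does a sensitivity analysis bring the death back?** SAP 7.5.2.2 lists three alternative censoring schemes for PFS.
- The first lifts truncation at subsequent therapy but otherwise keeps the primary rule: "PFS will be defined similarly to the primary definition except that events (progression or death) and disease assessments that occurred on or after subsequent" therapy are included. The baseline-scan exception stays.
- The second adds censoring after consecutive missed assessments.
- The third turns progression-free subjects lost to follow-up into events, which does not cover deaths.

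None restores it.

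**3. How many subjects?** Not given. Protocol 3.3.1 requires a measurable lesion and imaging within 28 days before randomization, so few or none are expected. SAP Appendix 7 counts 94 censored subjects across the arms for several pooled reasons, one of which is having no scans. The share without a *baseline* scan cannot be extracted from that.

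**4. Reproducing the stated power.** Inputs are from Protocol 8.1: 250 events, average HR 0.62, two-sided alpha 0.015 (z = 2.432), 1:1 within each comparison. By Schoenfeld's formula:

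power = Φ(|ln 0.62| × √250 / 2 − 2.432) = Φ(3.779 − 2.432) = Φ(1.347) = 0.911, against the stated 90%.

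The rows of the Appendix 7 table also reproduce within 2 points: 0.864 at 218 events (stated 85%), 0.817 at 195 (80%) and 0.767 at 175 (75%). A 4,000-run simulation of the SAP design model (control median 4 months, HR 0.55 after a 1-month delay, SAP accrual) gave power 0.903, with about 136 control-arm events at about 33 months.

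**5. Cost of one lost event under the 12-month fallback.** Appendix 7 has 102 control-arm events observed and about 8 more expected, hence 110, which is the table row with 195 events and 80% power. Write power = Φ(c√d − 2.432) and set c to match the stated value.
- 195 events, 80%: c = (2.432 + 0.842)/√195 = 0.2345. At 194 events, power is 79.76%, a loss of 0.24 points.
- 218 events, 85%: c = (2.432 + 1.036)/√218 = 0.2349. At 217 events, power is 84.81%, a loss of 0.19 points.

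This assumes that the lost events are spread over both arms.

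**6. If the deaths fall in one arm.** In the simulation at 250 events, k early control-arm events were turned into day-0 censorings:

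| k | Power | Median HR |
|---|---|---|
| 0 | 0.903 | 0.616 |
| 1 | 0.895 | 0.618 |
| 3 | 0.880 | 0.623 |

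Three control-arm deaths thus cost about 2.3 points (0.903 − 0.880). Three deaths spread at random over both arms left power at 0.902.

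**7. If the 136-event trigger were reached instead.** Missing control-arm events would then mainly delay the analysis. Assume that 1% of subjects never contribute an event. The expected 136th control-arm event moves from 32.9 to 33.3 months, about 12 days, with about 251 total events per comparison.

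**The case against.** **The effect is negligible, and the SAP is open about it.** Most of this stands. Baseline imaging is an eligibility requirement. The rule is pre-specified and the same in every arm. The count will be visible: "The status of subjects who are censored in the PFS KM analysis will be tabulated for each randomized treatment group using the following categories" that include a missing baseline scan. The deaths still count in OS and, under SAP 4.3.1, in PFS2/TSST. That limits the importance of the point, but it does not remove the contradiction.

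**A SAP may refine the protocol.** It may add detail. Here it reverses whether a primary event occurred, without saying so.

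**Censoring subjects without a baseline scan at day 0 is reasonable.** For those who do not have a qualifying death, this stands. A reader might infer a second fault, because the SAP also moves such subjects with later scans to day 0, where Protocol 8.3.1 would use the last evaluable assessment. The documents do not support that. Protocol Appendix 5 makes baseline tumor burden necessary for judging later progression, and it treats a lesion at a site not scanned at baseline as new disease. Without a baseline, later scans could be unusable or could produce spurious progression.

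**A reader might also infer that the SAP contains two rival primary definitions**, since Appendix 7 cites Section 8.3.1, a protocol section number. It does not. SAP 7.5.2.2 names Section 4.1.2 as the basis of the primary test. Appendix 7 cites 8.3.1 only for truncation at subsequent therapy, on which both texts agree. The mismatch is between protocol and SAP.

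**Conclusion.** The contradiction is real and can be seen from the text alone. It is minor. It concerns only deaths without a baseline scan, without earlier BICR progression and before subsequent therapy. It affects PFS in PD-L1 expressing subjects and in all randomized subjects.

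The size is probably nil or very small. That rests on the eligibility requirement, because no count is given. The per-event costs of 0.24 and 0.19 points assume losses spread over both arms and are not an upper limit: deaths concentrated in one arm cost more. The 2.3-point figure is for three control-arm deaths at 250 events, and nothing in the documents suggests that such a pattern occurred.

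A reader might infer that the rule favors the experimental arms. The documents do not show this. The direction depends on where any such deaths fall, and in the simulation censoring control-arm deaths moved the HR slightly toward 1.

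**What to change.** Before database lock:

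1. **SAP 4.1.2.** Replace the parenthesis that ends the baseline-scan sentence with: *unless they die without prior BICR PD and before any subsequent anti-cancer therapy, in which case the death is a PFS event on the date of death*. Check that Figure 4.1.2-1, which was not shown in the copy reviewed, has the same branch.
2. **SAP 7.5.2.1.** Change category 1a to: *no baseline scan and no death (or death with prior subsequent therapy)*. State that 1a is assigned before 1b, because a subject with neither a baseline nor an on-study scan would otherwise fit both.
3. **Leave the rest.** All other subjects without a baseline scan stay censored at day 0.
4. **Optional.** Keep the current rule as a sensitivity analysis.

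The cost is one clause, one category label with its order, and one programming condition. No new data are needed, and alpha and sample size do not change.
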